There is a precedent for using multiple agents for cervical ripening. Misoprostol and Foley combined have been shown to result in shorter times to delivery than Foley alone (8). However, not all authors have found a decreased time to delivery with this combination and have seen more uterine tachysystole with the addition of misoprostol (9). This unwanted effect with misoprostol is what causes many to favor agents besides misoprostol, despite that drug's low cost. The combination of the dinoprostone insert and Foley catheter for cervical ripening and labor induction has not been studied (Pubmed and clinicaltrials.gov searches using the terms "dinoprostone" AND "Foley" on July 23, 2016).

Here, we propose a pilot randomized trial to estimate the parameters necessary to accomplish the power calculation for a multicenter randomized controlled trial to compare the combined use of the dinoprostone vaginal insert and Foley catheter with Foley catheter alone for cervical ripening and labor induction in term pregnant women. In both this pilot study and the larger multicenter trial to follow, both efficacy and safety outcomes will be evaluated.

Hypothesis

In term women presenting for labor induction, combined use of the controlled release dinoprostone vaginal insert and Foley catheter for cervical ripening will decrease the median time from induction to vaginal delivery by at least four hours compared to the Foley catheter alone.

Objectives/Specific Aims

1. To estimate the median times from placement of ripening agents to vaginal delivery in both of the following groups:

- a. Dinoprostone vaginal insert and Foley catheter
 - b. Foley catheter alone
2. To evaluate the safety of the above combination by estimating in the above groups, stratified by parity (nulliparous or parous):
- a. Cesarean delivery rates
 - b. Uterine tachysystole rates
 - c. Puerperal infection rates
 - d. Oxytocin use rates
 - e. Neonatal ICU admission rates

Study Design Methodology

This is an open-label trial. The study will be approved by the local IRB. Women meeting enrollment criteria will be approached for enrollment. Those who provide informed consent will be allocated by an online randomization system either to placement of a transcervical Foley catheter and an intravaginal dinoprostone controlled release insert or a Foley catheter alone. Randomization will be stratified by parity (nulliparous or parous).

In both study groups, the balloon on the end of the Foley catheter will be inflated with 30 mL of sterile water, pulled back against the internal os of the cervix, and taped to the maternal thigh under minimal tension. Also in both groups, the Foley catheter will be removed if any of the following occurs: 1) expulsion, 2) fetal heart rate tracing mandating evaluation for membrane rupture and placement of internal monitors, 3) spontaneous membrane rupture, or 4) if 12 hours has elapsed since placement. The dinoprostone insert will be removed if: 1) the fetal heart rate tracing mandates evaluation for membrane rupture and placement of internal monitors, 2) tachysystole develops (more than 5 contractions per 10 minutes averaged over 30 minutes, 3) spontaneous membrane rupture, or 4) 12 hours has elapsed since placement. Though these are the criteria for insert removal, in keeping with the pragmatic design of this trial, the decision regarding removal will be left to the discretion of the attending physician.

Women will remain recumbent for 30 minutes after agent placement and, except for trips to the restroom, will undergo continuous monitoring of uterine contractions and fetal heart rate. Oxytocin, according to standard intravenous protocol, will be allowed only after removal of cervical ripening agent(s). After specified cervical ripening, labor management will be at the discretion of the attending obstetrician, in keeping with the pragmatic nature of the study design.

Antibiotics will be administered if indicated for prophylaxis against early-onset neonatal infection with group B streptococci or for treatment of chorioamnionitis. Cesarean delivery will be performed, per the discretion of the attending obstetrician, for standard maternal or fetal indications.

Medical records will be reviewed no less than 30 days after delivery. Demographic, intrapartum, and outcome data will be entered into a computerized database.

Primary Endpoint

Median time from placement of transcervical Foley catheter to vaginal delivery

Secondary Endpoints

1. Proportion of patients delivered by 12 hours
2. Proportion of patients delivered by 24 hours
3. Proportion of patients delivered vaginally by 12 hours
4. Proportion of patients delivered vaginally by 24 hours
5. Chorioamnionitis (defined as a temperature of 38C or higher and one or more of the following: maternal heart rate over 100, baseline fetal heart rate over 160, uterine tenderness, and/or purulent or foul-smelling cervical discharge)
6. Endometritis (defined as a postpartum temperature of 38C or higher on 2 or more occasions and no other source of fever apparent)
7. Wound infection (defined as a cesarean wound disruption and treatment with antibiotics for that indication); specifically excludes antibiotic treatment for “wound cellulitis” not associated with spontaneous or iatrogenic wound disruption
8. Puerperal infection (5, 6, or 7 above)
9. Cesarean delivery rate
10. Uterine tachysystole (defined as more than 5 contractions per 10 minutes, averaged over 30 minutes)
11. Neonatal information at delivery and discharge status (birth weight, Apgar scores, cord pH, NICU admission, other complications, neonatal death)

Sample Size

N=100

Inclusion Criteria

1. Cervix ≤ 2 cm dilated; if 2 cm, <80% effaced
2. Gestational age 37 weeks or more
3. Singleton gestation
4. Cephalic presentation
5. Live fetus

Exclusion Criteria

1. Contractions more frequent than every 5 minutes
2. Premature rupture of membranes
3. Prior uterine incision
4. Temperature 38C or higher
5. Fetal anomalies
6. Placenta previa
7. Suspected abruption or undiagnosed bleeding more than spotting
8. Fetal heart rate tracing prior to enrollment with no more than minimal variability, late decelerations, or more than two variable decelerations

9. HIV infection
10. Allergy to Prostaglandins
11. Clinical suspicion or definite evidence of fetal distress
12. Unexplained vaginal bleeding during this pregnancy
13. Evidence or strong suspicion of marker cephalopelvic disproportion
14. Oxytocic drugs are contraindicated
15. Already receiving intravenous oxytocic drugs
16. Multipara with 6 or more previous term pregnancies

Statistical Plan

This proposal is for a pilot study to estimate the parameters that will be used to inform the power calculation for a next-step multicenter randomized controlled trial. We will randomize, in a 1:1 ratio, stratifying 1:1 nulliparous and parous patients, 100 total patients to receive either:

1. Both the dinoprostone controlled release insert and a transcervical Foley catheter, or
2. Foley catheter alone

Patient characteristics and outcomes will be compared between the two study groups using two-sample t-tests for continuous measures and chi-square tests of association for categorical measures. Since time to delivery is known to not be a normally distributed outcome, we will estimate that parameter with medians and its variance with interquartile ranges.

Since this is a pilot study, we will estimate the outcomes to be evaluated in the planned next-step multicenter trial. Not surprisingly, the proposed sample size for this pilot study has less than 50% power to detect a 4-hour difference between groups. The rationale for stratifying a 1:1 ratio of nulliparous:parous patients is that doing so will maximize the precision with which the endpoints are estimated when stratified by parity.

Planned Publications

Results will be submitted for presentation at a national meeting, probably SMFM. Also, will submit results for publication as a full-length original article--probably *Obstetrics&Gynecology*.

Gender/Minority/Pediatric Inclusion for Research

Since only women become pregnant and undergo labor induction, all subjects in this study will be pregnant woman and fetus/infant dyads. The inclusion of minorities is anticipated in keeping with the racial/ethnic distribution of our obstetric population. Therefore, we anticipate including about 15% African-Americans, 45% Caucasians, 29% Hispanics, and 11% of other ethnicities.

Human Participants

We will enroll women age 18-50 who meet the above enrollment criteria. No specimens will be collected. Clinical data will be recorded at the time of enrollment. Clinical data also will be abstracted later from the medical record. A data collection form is attached.

Women with scheduled labor inductions will be screened by study personnel for eligibility. If

potentially eligible and the plan from the medical team is to begin the labor induction with cervical ripening using a Foley catheter, women will be approached about participation when the present for their scheduled induction. Since these women will not be in labor and it will be emphasized that participation is not required, coercion should not be an issue. Those women agreeing to participate will be consented by trained study personnel in their preferred language. We will have both English and Spanish consent forms. Those women who agree to participate will have a transcervical Foley catheter placed according to standard clinical practice. Once the Foley is placed, they will be randomized to either also have a Cervidil placed in the posterior vaginal fornix (according to package insert instructions) or not.

Because we will have consent forms in both English and Spanish, and since our patient population is 29% Hispanic, we anticipate enrolling non-English speaking participants. In addition to the Spanish consent form, hospital translation services will be utilized.

Since both Foley catheter and Cervidil are within the standard of care for starting labor inductions in the setting of an unfavorable cervix, risks associated with the study are anticipated to be no greater than the risks associated with pregnancy, labor induction and delivery. These include discomfort; abnormal labor progress, fetal heart rate tracing abnormalities, or other considerations leading to cesarean delivery; and postpartum complications such as hemorrhage or infection. Likelihood and seriousness should be no greater than similar patients not in the study who are undergoing labor induction.

To protect the privacy and confidentiality of research subjects, we will assign each participant a study ID number. This ID number will be linked to the patient's name and medical record number only via a key that will be maintained in a locked file drawer in the research coordinator's locked office. Once data collection is complete, the key will be destroyed, and the de-identified will not be able to be linked to participants.

The only potential benefit to subjects would be an increased likelihood of vaginal delivery or a shorter duration of labor induction if one of the treatment groups is superior. However, since this is a pilot study aimed at estimating the parameters needed for a next-step clinical trial, we do not anticipate a statistically significant difference in those outcomes in this study. The study, and participants' inclusion is important, since obtaining the data needed to conduct the next-step study will get us closer to optimizing labor inductions for future patients. Despite lack of a high likelihood of direct benefit, subject inclusion is reasonable since the risks are essentially the same as a labor induction if not included in the study.

Data and Safety Monitoring Plan

All adverse events will be reviewed by the PI and co-investigators and reported to the IRB according to institutional guidelines. All research data will be stored on a password-protected computer in the administrative offices of the Section of Maternal-Fetal Medicine. Any paper records and CRFs will be stored in a locked file drawer in the locked office of the research coordinator that is also located in the administrative offices of the Section of Maternal-Fetal Medicine. Since this study is a pilot including only 100 participants, we are not assembling a data and safety monitoring board.

References

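### Does the tachysystole rate lack a usable definition because no time window is stated and oxytocin use is absent from the endpoint list?

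*Combined protocol and SAP*

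**What the plan says.** Under Objectives/Specific Aims, Aim 2 lists five safety outcomes to be estimated by arm and stratified by parity, among them "Uterine tachysystole rates" and "Oxytocin use rates". Under Secondary Endpoints, item 10 is "Uterine tachysystole (defined as more than 5 contractions per 10 minutes, averaged over 30 minutes", with no observation period. Four of the five Aim 2 outcomes reappear in that list: cesarean delivery (item 9), tachysystole (10), puerperal infection (8) and NICU admission (within 11). Oxytocin use does not.

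Study Design Methodology provides for continuous monitoring of contractions in all women. It lists as one reason for removing the insert that "tachysystole develops (more than 5 contractions per 10 minutes averaged over 30 minutes", and leaves insert removal to the attending physician. On augmentation it says: "Oxytocin, according to standard intravenous protocol, will be allowed only after removal of cervical ripening agent(s". It calls the design pragmatic and leaves labor management after ripening to the attending obstetrician.

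On data, the same section says "Medical records will be reviewed no less than 30 days after delivery" and that intrapartum data go into the database. Human Participants refers to an attached data collection form and adds: "Once data collection is complete, the key will be destroyed".

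**The concern.** Tachysystole is a central safety question when a prostaglandin is added; the protocol's background names it as the reason many clinicians avoid misoprostol. It can occur during ripening or later, under oxytocin. Foley expulsion ends Foley use in both arms but is not a listed reason to remove the insert, so oxytocin may become available earlier with Foley alone. A rate counted over the whole labor then mixes two sources whose balance may differ by arm.

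The endpoint list does not say which rate is meant, and it omits the variable that would help to tell. The pilot's estimates are meant to inform a larger trial, so an unlabeled rate could be misused there. Destroying the key means that times not abstracted by then cannot be added. Because the trial is open label, one could also ask whether episodes will be charted alike in both arms.

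**Working it through.** The plan gives no rate, precision or power for tachysystole or oxytocin use, so there is no figure of its own to reproduce. Its one power statement concerns the 4-hour difference in time to delivery. From the documents come 100 women allocated 1:1 (50 per arm) and equal parity strata (25 per arm within a stratum). All rates below are assumptions.

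**1. What the plan yields as written.** The threshold and the monitoring are the same in both arms, and no phase is excluded. Followed literally, item 10 counts any episode between agent placement and delivery. The primary endpoint also starts at Foley placement, and randomization follows directly ("Once the Foley is placed, they will be randomized"), so the starting point is common to both arms.

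**2. Same later risk in both arms.** With ripening-phase risk *a* and later risk *b*, any-time risk = 1 - (1 - a)(1 - b). Take a = 10% (combination) and 2% (Foley alone).

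| b | Combination | Foley alone | Difference |
|---|---|---|---|
| 0% | 10.0% | 2.0% | 8.0 points |
| 10% | 1 - 0.90 × 0.90 = 19.0% | 1 - 0.98 × 0.90 = 11.8% | 7.2 points |
| 20% | 1 - 0.90 × 0.80 = 28.0% | 1 - 0.98 × 0.80 = 21.6% | 6.4 points |

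The difference moves by 8.0 - 6.4 = 1.6 points. The level moves far more: the Foley-alone rate goes from 2.0% to 21.6%.

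**3. Later risk that depends on oxytocin use.** Let *o* be the risk on oxytocin and *f* the share given it, so any-time risk = 1 - (1 - a)(1 - f × o). With o = 20%:

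- f = 60% (combination) and 90% (Foley alone): 1 - 0.90 × 0.88 = 20.8% and 1 - 0.98 × 0.82 = 19.6%, a difference of 1.2 points.
- f = 50% and 95%: 1 - 0.90 × 0.90 = 19.0% and 1 - 0.98 × 0.81 = 20.6%, a difference of -1.6 points.

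The window can therefore matter, but only if oxytocin use differs by 30 to 45 percentage points and carries a high risk.

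**4. Sampling error.** For 5/50 versus 1/50 the difference is 8 points, with a Newcombe 95% interval of -2.2 to 19.5, a half-width of (19.5 + 2.2)/2 = 10.9 points. For a single rate of 10%, 1.96 × √(0.1 × 0.9/n) gives 8.3 points at n = 50 and 11.8 points at n = 25. The 1.6-point shift in step 2 is small beside this. The most extreme shift in step 3, 8.0 + 1.6 = 9.6 points, is about as large as the half-width.

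**5. Would a restricted rate be better?** Two obvious candidates are not clearly so.

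- *Episodes before oxytocin, as a simple proportion.* Under a constant hourly hazard h the proportion is 1 - exp(-h × t). With h = 0.01 in both arms, 12 hours at risk gives 11.3% and 4 hours gives 3.9%, a risk ratio of 2.88 although the hourly rates are equal. The plan does not propose this split.
- *A fixed 12 hours from randomization.* A woman whose Foley is expelled early could receive oxytocin within that window, so it mixes the phases too.

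Isolating the ripening phase needs agent-removal times, because oxytocin may start well after removal or never.

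**The case for a change.** The strongest case for a change concerns the next trial. Two-sided 5%, 80% power and the pooled-variance formula n = [1.96 √(2p̄(1 - p̄)) + 0.8416 √(p₁(1 - p₁) + p₂(1 - p₂))]² / (p₁ - p₂)² give 138 per arm for 10% versus 2%, 394 for 19.0% versus 11.8%, and 714 for 28.0% versus 21.6%. A planner who took one rate for the other would be badly out, and a sentence of text would remove the doubt.

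It stands that the text is silent on the window and that a published rate needs its period stated. The rest is weaker. The protocol does not say that the next trial will be sized on tachysystole; the only effect size it states is four hours in time to delivery. Nor does it promise a ripening-phase rate. The step 3 shifts are not bias: if one strategy leads to less oxytocin, fewer episodes under oxytocin are part of that strategy's effect.

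Loss of data is not shown. The form that would settle it was not available to read, and the key is destroyed only after collection ends. That limit applies to any uncollected variable in a de-identified data set.

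Unequal charting is possible in an open-label trial, but nothing in the text establishes it. That tachysystole is a listed reason for insert removal does not mean an episode with Foley alone goes unrecorded or unmanaged.

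**Conclusion.** No change to the plan follows. The missing window is a gap that analysts will fill sensibly, by counting any episode from placement to delivery and saying so when they report. The missing oxytocin line is a clerical mismatch between two lists: Aim 2d already requires the estimate, by arm and parity.

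Under the assumed 10% and 2% ripening risks with equal later risk, the window changes the between-arm difference by at most 1.6 points, against a half-width of about 10.9 points. It can change more if oxytocin use differs greatly by arm, and the any-time rate then still answers the question of which strategy produces more tachysystole overall. The level of the rate does depend on the window, which is a matter of labeling the result.

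This conclusion rests on the any-time reading, on the continuous monitoring the protocol describes, and on assumed rates throughout. It takes no view on the rules for removing the agents or starting oxytocin.

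### The between-arm comparison uses neither parity, the randomisation stratum, nor the cervical dilation assessed for eligibility, so it may be less precise than the data allow; this is lost efficiency, not bias.

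*Combined protocol and SAP*

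**What the plan says.** The Statistical Plan sets the allocation: "We will randomize, in a 1:1 ratio, stratifying 1:1 nulliparous and parous patients, 100 total patients". Study Design Methodology names parity as the only stratification factor. The first inclusion criterion is "Cervix ≤ 2 cm dilated; if 2 cm, <80% effaced", so dilation has to be assessed in every woman before entry, and effacement only in those at 2 cm. Human Participants adds: "Clinical data will be recorded at the time of enrollment".

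For analysis, the Statistical Plan says "Patient characteristics and outcomes will be compared between the two study groups using two-sample t-tests for continuous measures", with chi-square tests for categorical measures. The next sentence treats time to delivery as non-normal and assigns it medians and interquartile ranges. No regression, covariate or stratified test is named for any between-arm comparison. Parity-stratified estimates are planned for the safety outcomes in the second aim.

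The Hypothesis is that the combination "will decrease the median time from induction to vaginal delivery by at least four hours compared to the Foley catheter alone". The Statistical Plan concedes that "the proposed sample size for this pilot study has less than 50% power to detect a 4-hour difference between groups".

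**The concern.** Both treatments act on the cervix, so its state at the start is a natural candidate predictor of time to delivery. Parity was thought important enough to stratify on, and the plan justifies the 1:1 parity mix on grounds of precision. Neither factor is carried into the comparison of arms.

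The two omissions work differently. Stratification already balances parity, so leaving it out mainly makes the reported standard error too large. Dilation is not balanced by design, so leaving it out lets chance differences in ripeness add real variability to the estimate. Testing baseline characteristics between randomised arms could reveal such a difference but would not remove it, and adjusting only after seeing one would be post hoc.

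At stake are the width of the interval around the 4-hour difference and the choice of spread handed to the next trial's power calculation.

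**Working it through.** **1. The plan's own power figure.** Neither the SD nor alpha is stated, so power below 50% cannot be reproduced. It can only be bounded. With n per arm and a two-sided 0.05 test (assumed), power for 4 h equals 50% when SD = 4 / (1.96 × √(2/n)).
- n = 50: 4 / (1.96 × 0.200) = 10.2 h.
- n = 40 (20% without the event, assumed): 9.1 h.

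The plan's statement is thus consistent with an SD above about 10.2 h at 50 per arm.

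**2. Inputs for the check.**
- From the documents: 100 women, 1:1 by arm and 1:1 by parity, taken as 25 per cell.
- Assumed: lognormal times; Foley-alone medians of 22 h (nulliparous) and 14 h (parous); within-parity log-SD 0.5; ratio of times 0.80; no cesareans; two-sided 0.05.
- A ratio of 0.80 means 0.20 × 22 = 4.4 h and 0.20 × 14 = 2.8 h, averaging 3.6 h, close to the 4-hour target.
- Assumed range: dilation explains R² = 0 to 0.30 of within-parity variance in log time.

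**3. Formula.** Effect = −ln 0.80 = 0.223. SE = √(V × 2/50). Power ≈ Φ(effect/SE − 1.96).
- Unadjusted: V = 0.5² + (ln(22/14))²/4 = 0.250 + 0.051 = 0.301.
- Parity: V = 0.250.
- Parity plus dilation: V = 0.250 × (1 − R²).

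| Analysis | SE | Power, normal | Power, t reference |
|---|---|---|---|
| Unadjusted | 0.110 | 52.9% | 52.1% |
| Parity | 0.100 | 60.7% | 59.8% |
| + dilation, R² 0.05 | 0.097 | 62.9% | 62.0% |
| + dilation, R² 0.10 | 0.095 | 65.3% | 64.4% |
| + dilation, R² 0.20 | 0.089 | 70.4% | 69.5% |
| + dilation, R² 0.30 | 0.084 | 76.0% | 75.2% |

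Simulation of the same set-up, with dilation at 0, 1 or 2 cm, agrees: about 52% unadjusted, 59–60% with parity, and about 63–65%, 69–70% and 75% with dilation. At R² of 0.05 or less, dilation adds at most about 2 points. At zero it costs less than 1 point.

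**4. A scenario that meets the plan's statement.** The 52% above is slightly over the plan's bound. With log-SD 0.65, V is 0.4225 + 0.051 = 0.474 unadjusted and 0.4225 with parity. Normal-approximation power is then 36.7% unadjusted, 40.4% with parity, and 44.0%, 48.4% and 53.6% with dilation at R² 0.10, 0.20 and 0.30. The pattern is the same at a lower level.

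**5. Chance imbalance in dilation.** The standardised baseline difference has SE √(2/50) = 0.20, so its 95% range is about ±0.39 SD. About 32% of randomisations exceed 0.2 SD. The shift in the time difference at that limit is 1.96 × 0.20 × ρ × SD. With SD 10.2 h this is 0.4 h at ρ = 0.1, 1.2 h at ρ = 0.3 and 2.0 h at ρ = 0.5. The ρ values are assumed.

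**6. Spread for the next trial.** Required sample size is proportional to V. At R² 0.20 the residual V is 0.200, against 0.301 unadjusted, a ratio of 0.66. A trial sized on the residual spread but analysed unadjusted would have about two thirds of the women it needs. A trial sized on the unadjusted spread but analysed with adjustment would be about 1.5 times larger than needed (0.301 / 0.200).

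**The case against.** The strongest reply is that this is a pilot. Its first aim is the median time in each arm, no primary between-arm effect estimate is defined, and the sponsor writes that "we do not anticipate a statistically significant difference in those outcomes in this study". The t-test sentence is general, and time to delivery is handled in the sentence after it. Adjustment does little for a marginal arm median. All of this stands, and it is why the adjusted estimate belongs beside the medians and not in their place. But the Hypothesis is about a difference, and the pilot's numbers are meant to size a trial of that difference.

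The second reply is that dilation's prognostic strength is not shown. Eligibility confines it to 0–2 cm, which may weaken it. At a correlation of 0.3 or below, the SE falls by less than 5% (1 − √(1 − 0.09) = 4.6%). This also stands. In the worked scenario, parity accounts for the first 8 points or so of power, and dilation may add little.

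A reader might infer that the unadjusted comparison is biased, or that an imbalance in ripeness would invalidate it. The documents do not support that. Under randomisation such an imbalance is random error, which the unadjusted standard error already covers on average. A reader might also infer that no new data are needed. That cannot be confirmed: eligibility requires only a threshold, and the data collection form is not among the pages available for review.

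**Conclusion.** The omission is certain: no between-arm comparison in the plan uses parity or baseline dilation. The consequence is reduced efficiency. The arm medians remain valid and the pilot is not undermined.

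The size of the loss is uncertain. Under the main assumptions (lognormal times, log-SD 0.5, ratio 0.80, no cesareans), parity raises power from about 52% to 60%. Dilation raises it further to between 60% and 75% as R² runs from 0 to 0.30. These figures come from a log-time model standing in for a comparison that the plan does not define, and they would change if women delivered by cesarean were excluded or censored. The documents do not support calling dilation a strong predictor in this population. The case for change rests on low cost and a very small downside, not on a proven large gain.

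**What to change.** - Keep the unadjusted medians and interquartile ranges by arm as planned.
- Prespecify one supporting between-arm estimate of time to delivery, with a confidence interval, adjusted for parity and baseline dilation. Median regression gives the difference in hours, to be read against the 4-hour target; a log-time model is the alternative. Apply whatever rule is adopted for women delivered by cesarean.
- First confirm that the data collection form records dilation in centimetres at enrolment. If it does not, add the field; until then, adjust for parity alone.
- Present baseline characteristics descriptively, without significance tests.
- Report both the unadjusted and the residual spread. Use the residual spread in the next trial's power calculation only if that trial will make the same adjustment; otherwise use the unadjusted spread.

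The cost is two or three sentences in the Statistical Plan, a few lines of code and, at most, one field on the form. No additional examination is needed.

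### Aim 2 is to estimate safety rates by arm and parity, but the only between-arm method stated for them is a chi-square test, with no effect estimate or confidence interval

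*Combined protocol and SAP*

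**What the plan says.** Objectives/Specific Aims, Aim 2: "To evaluate the safety of the above combination by estimating in the above groups, stratified by parity (nulliparous or parous"), followed by five rates: cesarean, tachysystole, puerperal infection, oxytocin use and NICU admission.

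The Statistical Plan fixes the numbers: "We will randomize, in a 1:1 ratio, stratifying 1:1 nulliparous and parous patients, 100 total patients". Patient characteristics and outcomes are then compared between the two groups by t-tests if continuous and by "chi-square tests of association for categorical measures". For time to delivery the plan adds a median and an interquartile range. For the binary outcomes it adds nothing: no risk difference or ratio, no interval, no method for small counts, and no method for the parity-stratified results that Aim 2 calls for.

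The plan states its purpose as estimation: "we will estimate the outcomes to be evaluated in the planned next-step multicenter trial". It admits "less than 50% power to detect a 4-hour difference between groups", which concerns time to delivery only. In Human Participants, after naming a greater chance of vaginal delivery and a shorter induction as possible benefits, it says "we do not anticipate a statistically significant difference in those outcomes in this study". The background states that "The combination of the dinoprostone insert and Foley catheter for cervical ripening and labor induction has not been studied", and that some authors who combined misoprostol with a Foley "have seen more uterine tachysystole with the addition of misoprostol".

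**The concern.** The aim and the method answer different questions. The aim asks what the safety rates are in each arm and parity group. A chi-square test asks only whether the data are inconsistent with no difference. In a pilot of this size a non-significant result can arise because there is no increase, or because there is an important increase that the sample could not show. The p-value does not separate the two.

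The gap matters more for safety than for efficacy. By the plan's own account the combination is unstudied, a related combination raised a tachysystole signal, and the results are meant to inform a multicenter trial. That trial's planners need the size of any excess and its uncertainty. The stated low-power caution covers the 4-hour difference. The later remark on significance reaches cesarean indirectly, through likelihood of vaginal delivery. Neither reaches tachysystole, infection or NICU admission.

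**Working it through.** **Inputs from the documents.** N = 100, allocated 1:1, so 50 per arm. Nulliparous and parous women are enrolled 1:1, so 100/4 = 25 per arm in each parity stratum.

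**Inputs assumed.** The documents give no event rates, significance level or dropout. I use a two-sided 5% level, no dropout, and a range of rate pairs (Foley alone versus combination).

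**The plan's own power figure.** This is for time to delivery, not safety. It cannot be reproduced because no standard deviation is given. With a normal approximation, power = Φ(4/(SD·√(2/50)) − 1.96). This equals 50% when 4/(0.2·SD) = 1.96, so SD = 20/1.96 = 10.2 hours. The statement is consistent with any SD above about 10.2 hours at 50 per arm. No power figure is stated for any safety outcome.

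**Power of the stated test.** For x events of n in one arm and y of n in the other, the uncorrected statistic is X² = 2n·[x(n−y) − y(n−x)]² / [n²·(x+y)·(2n−x−y)]. Power is the sum of the binomial probabilities of all (x, y) with X² > 3.84.

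| Foley alone vs combination (assumed) | Rise, points | Power, 50 per arm | Power, 25 per arm |
|---|---|---|---|
| 5% vs 10% | 5 | 14.5% | 8% |
| 25% vs 35% | 10 | 19% | 13% |
| 10% vs 20% | 10 | 30% | 17% |
| 5% vs 15% | 10 | 39% | 21% |
| 10% vs 25% | 15 | 53% | 30% |
| 5% vs 20% | 15 | 66% | 38% |
| 10% vs 30% | 20 | 73% | 45% |
| 25% vs 50% | 25 | 75% | 48% |
| 5% vs 25% | 20 | 85% | 56% |

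The plan names a test between the two groups as a whole, so the 50-per-arm column applies to it. The last column shows only how little a test could do inside a stratum; the plan does not name such a test.

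**What the p-value hides.** Take 6/50 on the combination and 3/50 on Foley alone (illustrative counts).

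- X² = 100·(6·47 − 3·44)² / (50·50·9·91) = 100·150²/2,047,500 = 1.10, so p = 0.29.
- Risk difference = 12% − 6% = +6.0 points.
- Wilson limits are 5.6% to 23.8% for 6/50 and 2.1% to 16.2% for 3/50.
- Newcombe lower limit = 6.0 − √((12.0−5.6)² + (16.2−6.0)²) = −6.0 points.
- Newcombe upper limit = 6.0 + √((23.8−12.0)² + (6.0−2.1)²) = +18.4 points.

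The test reports p = 0.29. The interval reports that an increase of up to about 18 points is not excluded. Within a stratum, 3/25 versus 1/25 gives p = 0.30 and a difference of +8.0 points (−9.4 to +26.3).

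**Small counts.** With 9 events in 100 women the expected count is 9/2 = 4.5 per arm, below the usual guide of 5. The chi-square approximation is therefore weak for rare outcomes.

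**The case against.** The strongest reply is that this is a declared pilot whose purpose is estimation. Aim 2 itself says the safety rates are to be estimated, low power is expected in such a design, and any reader given events and denominators can compute an interval. Much of this stands: low power is not the defect. But it supports the change, because an estimation study should specify how it will express uncertainty, and for the binary outcomes this plan does not.

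Three stronger readings are tempting, and the documents do not support them.

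- A reader might infer that the safety test has power below 40% throughout. That holds only for the assumed rises of 5 to 10 points. For the assumed rises of 15 to 25 points, power is 53% to 85% at 50 per arm. The lowest values come from a within-stratum test that the plan does not name.
- A reader might infer that a non-significant result will be reported as safe. Nothing in the documents says so, and there is no go/no-go safety rule. The plan is silent on interpretation, which is a gap and not a commitment to misread.
- A reader might infer that no caution applies to any safety outcome. The Human Participants remark on likelihood of vaginal delivery partly covers cesarean.

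**Conclusion.** The point holds as a mismatch between an estimation aim and a comparison specified only as a test. Chi-square is the only between-arm method stated for the Aim 2 outcomes, and no effect estimate or interval for them appears anywhere in the document.

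Its size depends on assumed rates. At 50 per arm and a two-sided 5% level, a rise of 5 to 10 points in the pairs examined would be non-significant in roughly 61% to 86% of trials (100% − 39.3% to 100% − 14.5%). Larger rises would be detected more often than not. The consequence is a safety table that leaves out the size of increase still compatible with the data. This is a worthwhile correction to the analysis plan; it does not invalidate the design.

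**What to change.** In the Statistical Plan, make the main between-arm summary for each Aim 2 outcome the events/N by arm with the risk difference (combination minus Foley alone) and its 95% Newcombe or Miettinen-Nurminen interval. Report it overall and within each parity stratum. Either interval is better suited to small counts than the chi-square approximation. Chi-square p-values may stay as descriptive. Add one sentence saying that a non-significant test will not be read as evidence of no increase.

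The cost is plan wording and extra table columns, with no additional patients or data. The price is a less favourable safety statement: in the 6/50 versus 3/50 example, the report would say that an increase of up to about 18 points is not excluded. The interval adds no power; it makes the remaining uncertainty visible.
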